3 SYNOPSIS

Protocol Number:

TLC590A1001

Title:

A Phase I/II, Randomized, Double-blind, Comparator-controlled, Dose-escalation Study to Evaluate the Safety, Pharmacokinetics, and Efficacy of TLC590 for Postsurgical Pain Management Following Inguinal Hernia Repair

Investigational Product:

TLC590 (Ropivacaine Liposome Injectable Suspension)

Study Centers:

Approximately 2 centers in the United States (US)

Phase:

Phase I/II

Objectives:

The primary objective of this study is to evaluate the safety and tolerability of TLC590 for postsurgical pain management in subjects with inguinal hernia repair surgery.

The secondary objectives of this study are:

- To evaluate the pharmacokinetic (PK) profile and dose-exposure relationship of TLC590, as well as the bioavailability as compared with Naropin®.
- To evaluate analgesic efficacy of TLC590 compared with Naropin® for postsurgical pain management in subjects with inguinal hernia repair surgery.
- To evaluate the exposure-response relationship between PK parameters and pain management.

Study Design:

This is a Phase I/II, randomized, double-blind, comparator-controlled, dose-escalation study to assess the safety, PK, and efficacy of single postsurgical application of TLC590 compared with Naropin® via a single infiltrative local administration in adult subjects following inguinal hernia repair surgery.

The study will enroll approximately 64 evaluable subjects who meet all entry criteria across 4 cohorts.

Approximately 16 subjects will be enrolled to each cohort in a 3:1 ratio. Each cohort will comprise 12 subjects receiving a dose of TLC590 and 4 subjects receiving active comparator drug (Naropin® 150 mg; [0.5%, 5 mg/mL]) in accordance with the randomization schedule (as assigned by a centralized interactive web response system [IWRS]) and dose-escalation scheme outlined in the following table.

Cohort	TLC590	Naropin®
Cohort 1 (N = 16)	N = 12: TLC590; 190 mg (10 mL)	N = 4: Naropin®; 150 mg (30 mL)
Cohort 2 (N = 16)	N = 12: TLC590; 380 mg (20 mL)	N = 4: Naropin®; 150 mg (30 mL)
Cohort 3 (N = 16)	N = 12: TLC590; 570 mg (30 mL)	N = 4: Naropin®; 150 mg (30 mL)
Cohort 4 (N = 16)	N = 12: TLC590; 760 mg (40 mL) OR N = 12: TLC590; 475 mg (25 mL); if the TLC590 570 mg (30 mL) dose is not tolerated	N = 4: Naropin®; 150 mg (30 mL)

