 - Commits to the use of an acceptable form of birth control or be surgically sterile; or be at least 2 years post-menopausal; or is practicing double-barrier contraception; or practicing abstinence (must agree to use double-barrier contraception in the event of sexual activity); or using an insertable, injectable, transdermal, or combination oral contraceptive approved by the FDA for greater than 2 months prior to Screening visits and commits to the use of an acceptable form of birth control for the duration of the study and for 30 days from completion of the study.
6. Male subjects must be sterile (biologically or surgically) or commit to the use of a reliable method of birth control (e.g., must agree to use double-barrier contraception in the event of sexual activity) for the duration of the study until at least 1 week after the administration of blinded study medication.
7. Have a body mass index $\leq 35 \text{ kg/m}^2$.

Statistical Analysis:

No formal sample size calculation will be performed, but rather, the number of subjects per cohort is based on previous experience with other drugs for first-in-human trials and is generally considered adequate for determination of tolerability and PK characterization.

NPRS scores following rescue analgesics will be imputed by the windowed worst observation carried forward. The worst NPRS score prior to each rescue analgesic will be carried forward within the following 4-hour window. If the pain intensity score for the windowed observation is higher than the worst observed score, it will not be replaced. Missing NPRS scores will be imputed via the last observation carried forward (LOCF) using the last observed scores. Sensitivity analyses on NPRS related endpoints will be performed by imputing data following rescue analgesics using LOCF. The NPRS scores just prior to the rescue analgesics will be carried forward for all subsequent scheduled assessments.

Analysis of variance (ANOVA) or a Kruskal-Wallis test (if the normality assumption is not met) will be used to assess the overall difference among treatments for NPRS at rest and with movement, AUC of NPRS at rest and with movement, the total postoperative consumption of rescue analgesics, and the average daily rescue analgesic consumption.

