The Kaplan-Meier method will be used to analyze time to the first postoperative use of rescue analgesic, and time to the first postoperative use of rescue opioid. Comparison of the survival curves among treatments will be assessed by a log-rank test.

Chi-square test or Fisher's exact test will be used to assess the overall differences among treatments for the proportions of subject who are opioid free, subjects who used no rescue analgesics, and subjects who used no postoperative antiemetic therapy, and PGA.

All the exploratory endpoints will be summarized descriptively.

Blood concentrations of ropivacaine (unbound and total) will be descriptively summarized at each scheduled time of PK sampling by treatment. PK parameters will be derived by non-compartmental analysis.

The dose-exposure relationship of TLC590 will be evaluated by the tabulation of AUC and C_{max} parameters obtained from each dose level and displayed graphically. The power model will be used to investigate the dose proportionality for subjects who received the TLC590 treatment. The relative systemic bioavailability (including relative AUC and C_{max}) compared to Naropin[®] will be analyzed by using a general linear model (GLM). Exposure-response relationship between PK parameters and NPRS scores will be displayed graphically and will be evaluated accordingly.

Safety analysis will be based on all safety information collected including physical examination, surgical site assessment, vital signs assessments, clinical laboratory data, 12-lead electrocardiogram (ECG), AEs, and SAEs.

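### Does the plan need an NPRS analysis that leaves post-rescue scores as recorded?

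*Combined protocol and SAP*

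**What the plan says.** All of this is in Section 3, Synopsis.

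- Main rule after rescue: "The worst NPRS score prior to each rescue analgesic will be carried forward within the following 4-hour window". There is one exception: "If the pain intensity score for the windowed observation is higher than the worst observed score, it will not be replaced".
- Sensitivity rule: "Sensitivity analyses on NPRS related endpoints will be performed by imputing data following rescue analgesics using LOCF", defined by "The NPRS scores just prior to the rescue analgesics will be carried forward for all subsequent scheduled assessments".
- Use of the scores: ANOVA or Kruskal-Wallis "will be used to assess the overall difference among treatments for NPRS at rest and with movement", and likewise for the NPRS AUCs.
- Rescue as an outcome: total and average daily consumption are tested. For timing, "The Kaplan-Meier method will be used to analyze time to the first postoperative use of rescue analgesic", and time to first rescue opioid is handled the same way. The proportions who are opioid free and who use no rescue are also compared.
- Place of efficacy: "The primary objective of this study is to evaluate the safety and tolerability of TLC590"; analgesic efficacy against Naropin is among the secondary objectives. No formal sample size calculation was made. Dose escalation rests on the safety committee's review of adverse events, with PK data, not on NPRS.

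The text supplied for review is the synopsis only. It names no analysis of NPRS or NPRS AUC with post-rescue scores as recorded.

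**The concern.** A sensitivity analysis should vary the assumption in doubt. The assumption here is that recorded post-rescue scores should be overwritten, and both planned analyses make it. If Naropin subjects take more rescue, more of their scores are raised, and part of the NPRS AUC difference comes from the rule. Agreement between the two analyses could be taken for robustness although both rest on replaced scores. Disagreement could come from the unlimited carry-forward alone. The rescue endpoints show whether rescue use differs by arm, but not how many NPRS points replacement added. At stake is the reading of the secondary pain comparison.

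**Working it through.** **The plan's own figure.** "Each cohort will comprise 12 subjects receiving a dose of TLC590 and 4 subjects receiving active comparator drug". Over four cohorts, 4 × (12 + 4) = 64, as stated. That gives 12 subjects per TLC590 dose and, if pooled over cohorts (an assumption), 4 × 4 = 16 on Naropin.

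**The two rules side by side.** They differ in three ways: duration (4 hours, or all later assessments), carried value (worst earlier score, or score just before rescue), and the keep-the-higher exception (present only in the main rule). The sensitivity rule is therefore not simply a longer version of the main one. Two worked profiles show this, with assumed assessments at 1, 2, 4, 8, 12, 24, 36 and 48 h, one rescue at 4 h, and trapezoidal AUC:

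| Recorded scores | As recorded | Main | Carry to end |
|---|---|---|---|
| 5, 7, 6, 3, 3, 2, 2, 1 | 121 | 137 | 283 |
| 3, 4, 4, 3, 7, 6, 5, 4 | 243.5 | 247.5 | 187.5 |

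In the first profile, as recorded is 6 + 13 + 18 + 12 + 30 + 24 + 18 = 121. The main rule lifts the 8 h score from 3 to 7, giving 6 + 13 + 26 + 20 + 30 + 24 + 18 = 137. Carrying 6 forward gives 6 + 13 + 6 × 44 = 283. The carry-to-end result can lie above or below both others, so it does not bound the as-recorded result.

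**How far as-recorded departs from main.** The grid had 192 assumed scenarios: analgesia of about 6 h on Naropin against 12 or 20 h on TLC590; three pain shapes; four rescue thresholds; two rescue effects; AUC to 48 or 72 h; two schedules. The as-recorded AUC difference was smaller than main in all 192, at 0.27 to 0.78 of it (median 0.53). The direction is largely built in, because rescue lowers scores, the rule only raises them, and the less effective arm takes more rescue. Both readings of carry-to-end (from the first rescue, or from each) came within 5% of main in 19 of 192, with as-recorded 28% to 65% lower. At trial size, with no drug difference, every rule rejected in about 4% to 5% of trials at an assumed 0.05 level.

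**Would as-recorded show the share due to replacement?** That needs a third quantity, the difference had no one taken rescue. Main minus as-recorded splits into masking (rescue-free minus as-recorded) and inflation (main minus rescue-free).

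With rescue triggered by pain, as ratios to the rescue-free difference (medians, so the split is approximate):

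- 96 scenarios: main 1.14 (0.85 to 1.44), as-recorded 0.63 (0.25 to 0.89). Gap 0.51; masking 1 − 0.63 = 0.37, or 73%.
- A separate 48 scenarios: main 1.19 (1.04 to 1.48), as-recorded 0.65 (0.26 to 0.89). Gap 0.54; masking 0.35, or 65%.

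With rescue assigned regardless of pain, 40% of TLC590 and 90% of Naropin subjects rescued, and AUC over 1 to 48 h, the rescue-free difference is about 47 h × the underlying point difference (Monte Carlo error about 1):

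| Point difference | Rescue effect | Rescue-free | As recorded | Main | Masking share of gap |
|---|---|---|---|---|---|
| 0 | 1 | 0 | −2.3 | 4.4 | 2.3/6.7 = 34% |
| 0 | 2 | 0 | −4.6 | 5.1 | 4.6/9.7 = 47% |
| 1 | 1 | 47 | 43.9 | 51.1 | 3.1/7.2 = 43% |
| 1 | 2 | 47 | 39.4 | 49.1 | 7.6/9.7 = 78% |

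As-recorded falls below the rescue-free value and main above it in every row, and the split runs from about a third to nearly four fifths. The gap between the two analyses therefore cannot be read as the amount added by replacement. With 80% rescued in both arms, main added only 0.1 to 0.7 to the as-recorded difference.

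**The case for a change.** The strongest case for a change is that the addition costs two sentences and one run. The recorded scores must already exist, since the main rule compares each of them with the worst earlier score. With assumed longer TLC590 analgesia, the overall ANOVA was significant in 63% to 64% of simulated trials under main and 41% to 46% as recorded. When main and carry-to-end were both significant, as-recorded was not in 31% to 39%. The main rule is not always nearer the rescue-free value either: in the two zero-difference rows above, as-recorded is the closer.

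Some of this stands. The planned pair does not show the unreplaced result, and agreement between the two should not by itself be reported as robustness. The rest carries less weight. The lower rate of significance is what masking by rescue would produce, and part of the discordance is ordinary chance at low power. The zero-difference rows assume 40% against 90% rescue with no difference in pain, an artificial case, and such an imbalance would show plainly in the rescue endpoints. Low cost makes a table easy to add; it does not make its absence an error.

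**Conclusion.** No change. The reading of the text is right: both rules overwrite recorded post-rescue scores, and the synopsis names no as-recorded analysis. But the main rule is a reasonable choice that should stay, it produced no excess of false positives in the simulations, and rescue use is analysed separately through consumption, timing and proportions. Efficacy is secondary, without a formal sample size, and neither the primary safety objective nor dose escalation depends on NPRS.

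The as-recorded difference would usually be smaller, at 0.27 to 0.78 of main in the 192 scenarios. It describes pain including the effect of rescue, and would not give the share of the difference due to replacement. All these sizes rest on assumed pain profiles, rescue behaviour and schedules, so only the direction is reliable, and only where rescue use differs between arms. An analyst who wants the table can produce it as a labelled supplement from data in hand, and a fuller statistical section than the synopsis may already include it.

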Dose escalation of a single postsurgical administration of TLC590 will be performed using sequential dose levels starting at 190 mg up to 760 mg, as compared with Naropin® 150 mg (5 mg/mL) via infiltrative local administration in adult subjects following unilateral Lichtenstein inguinal hernia repair surgery. Dose escalation

will be determined by review of treatment-related adverse events and all serious AEs (SAEs) by a safety monitoring committee (SMC); PK data will also be reviewed only by the SMC at the end of each cohort to assess systemic exposure to total and free (unbound) ropivacaine.

Number of Subjects:

Approximately 64 evaluable subjects in up to 4 cohorts of approximately 16 subjects per cohort will be enrolled in this study.

Treatment:

At the end of the surgery, prior to wound closure, a single infiltrative local dose of blinded study medication will be administered.

Study Duration:

The study duration will be approximately 60 days. Each subject will be screened within 28 days before blinded study medication administration. At the end of the surgery, prior to wound closure, a single infiltrative local dose of blinded study medication will be administered. The subject will remain in the clinic at least 48 hours after administration of blinded study medication, and each subject will be followed for 30 days.

Study Population:

Inclusion Criteria:

To be eligible for study entry, subjects must satisfy all of the following criteria:

1. Able and willing to provide a written informed consent, indicating that he/she is aware of the investigational nature of this study involved and willing to comply with the requirements of this study protocol.
2. Male or female between 18 and 65 years of age, inclusive.
3. Scheduled to undergo a primary, unilateral Lichtenstein inguinal hernia repair with mesh, and be able to use the anesthesia regimen.
4. Have an American Society of Anesthesiology (ASA) Physical Status Classification of 1 or 2.
5. Female subjects are eligible only if all of the following apply:
 - Not pregnant (female subjects of childbearing potential must have a negative serum pregnancy test at Screening and negative urine pregnancy test at Baseline before randomization);
 - Not lactating;
 - Not planning to become pregnant during the study;

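### The efficacy tests named in the synopsis compare all treatments at once; no TLC590-versus-Naropin estimate or confidence interval is specified, although that comparison is the stated efficacy objective

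*Combined protocol and SAP*

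**What the plan says.** All references are to section 3 (Synopsis), the only part of the combined protocol and SAP available here.

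- **Objectives.** One secondary objective reads "To evaluate analgesic efficacy of TLC590 compared with Naropin". The dose-escalation text repeats the comparison: "as compared with Naropin® 150 mg (5 mg/mL) via infiltrative local administration".
- **Study Design.** "Each cohort will comprise 12 subjects receiving a dose of TLC590 and 4 subjects receiving active comparator drug". Naropin is 150 mg in all four cohorts.
- **Statistical Analysis, pain scores and rescue consumption.** ANOVA or Kruskal-Wallis "will be used to assess the overall difference among treatments for NPRS at rest and with movement". The same sentence covers the NPRS areas under the curve and rescue consumption.
- **Statistical Analysis, time to rescue.** "Comparison of the survival curves among treatments will be assessed by a log-rank test".
- **Statistical Analysis, proportions and PGA.** Chi-square or Fisher's exact test "will be used to assess the overall differences among treatments for the proportions of subject who are opioid free", and likewise for the other proportions and PGA.
- **Statistical Analysis, PK.** Relative AUC and Cmax "compared to Naropin[®] will be analyzed by using a general linear model (GLM)". This is the only analysis set explicitly against Naropin.
- **Sample size.** "No formal sample size calculation will be performed".

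For efficacy, the Synopsis names no pairwise contrast, effect estimate, confidence interval, trend test or multiplicity rule. It does not say whether the Naropin subjects from the four cohorts are pooled.

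**The concern.** The objective asks a directed question: how does TLC590 compare with Naropin? The named tests answer a different one: are the treatments all alike? Rejecting that hypothesis could mean that one dose beats Naropin, that one dose is worse than Naropin, or that the TLC590 doses differ from each other while their average equals Naropin. The p-value is the same kind of evidence in each case.

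Followed exactly, the plan would end with a p-value per endpoint and no prespecified measure of the effect that the objective names. Contrasts would then be chosen after unblinding, or readers would judge from group summaries that carry no stated uncertainty for the comparison. The PK paragraph does name a comparison with Naropin, so brevity alone does not explain why the efficacy paragraphs lack one.

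**Working it through.** **The plan's own figure.** 4 cohorts × (12 + 4) = 64 subjects, and 12:4 = 3:1. Both agree with the Synopsis. It states no significance level, power, effect size or SD, so there is no power figure to reproduce.

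**Assumptions.** Two-sided 5%; equal SD, with effects in SD units; all four cohorts enrolled; Naropin pooled. This gives five groups of 12, 12, 12, 12 and 16.

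**1. The overall test does not see sign or location.** ANOVA power depends on λ = Σ nᵢ(μᵢ − μ̄)², where μ̄ is the weighted mean.

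- One dose 1 SD above the rest: μ̄ = 12/64 = 0.1875, so λ = 12(0.8125)² + 52(0.1875)² = 7.92 + 1.83 = 9.75.
- One dose 1 SD below the rest: μ̄ = −0.1875 and λ is again 9.75. It does not matter which dose is shifted, because all doses have 12 subjects.
- With 4 and 59 degrees of freedom (critical F = 2.53), power is 0.664 in both cases.
- Two doses 0.8 SD better and two 0.8 SD worse: μ̄ = 0 and λ = 48 × 0.64 = 30.72, with power above 0.99. The average TLC590-minus-Naropin difference is zero.

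**2. The same for proportions.** Take 6/12 at three doses and 8/16 on Naropin. With the fourth dose at 11/12 or at 1/12, chi-square is 6.94 on 4 df (p = 0.14) both times. The differences from Naropin are opposite: +42 points (Newcombe 95% interval 7 to 65) and −42 points (−65 to −7). The overall result here is not significant; the example shows only that the statistic carries no direction.

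**3. What the missing estimates would deliver.** Half-width = critical value × standard error, in SD units.

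| Comparison | Standard error | Critical value | Half-width |
|---|---|---|---|
| One dose v pooled Naropin, unadjusted | √(1/12 + 1/16) = 0.382 | t₅₉ = 2.001 | 0.76 |
| Same, Dunnett over four doses | 0.382 | 2.526 | 0.96 |
| One dose v Naropin, fixed cohort effects | √(1/12 + 1/4) = 0.577 | t₅₆ = 2.003 | 1.16 |

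For an assumed NPRS SD of 2 to 3 points, 0.76 SD is ±1.5 to ±2.3 points. If both proportions are 50%, the Newcombe half-width (12 v 16) is about 33 points. For time to rescue, the limits are the hazard ratio divided and multiplied by exp(1.96 × √(1/12 + 1/16)) = 2.1 if every subject has the event.

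**4. The price of leaving intervals unadjusted.** With a shared control, the chance that at least one of four unadjusted 95% intervals excludes zero when no dose differs is about 16% per endpoint (simulation). In the example in step 2, a four-dose Dunnett critical value (about 2.45, large-sample) in the same Newcombe formula widens 7 to 65 points to about −2 to 69, which includes zero.

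**The case against.** The best counter-argument is that the point rests on silence in a summary. Contrasts, intervals and the handling of pooled controls usually belong in the statistical section or SAP. A reader might infer that the trial has no planned comparison with Naropin at all. The available text does not support that: the sections where it would appear were not available, and the log-rank sentence says only that curves are compared among treatments, which does not exclude pairwise use.

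The stakes are also modest. Efficacy is secondary, the cohort size was chosen for tolerability and PK, and escalation rests on adverse events and PK. Group summaries and Kaplan-Meier curves would show direction informally. An overall test is a defensible exploratory choice.

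A further objection is that a full set of unadjusted intervals invites false signals. That stands, and the remedy has to state it.

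What survives is narrower. The Synopsis does commit to efficacy tests, and those tests do not answer the objective it states. In a study with no formal sample size, an estimate with its interval tells the reader more than a bare overall p-value.

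**Conclusion.** The point holds as a cheap improvement to the analysis plan. As the Synopsis stands, a significant efficacy result would not identify the dose, the direction or the size of any difference from Naropin. The 66% power figure for either direction illustrates this under the stated assumptions (12 per dose, 16 pooled Naropin, 1 SD at one dose, two-sided 5%). The insensitivity to sign does not depend on those numbers.

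Two stronger readings should be resisted. One is that the overall tests are wrong or lack power and should be replaced: the argument is about interpretation, and the Synopsis sets no power target against which to judge them. The other is that the gap undermines the trial's main conclusions: the primary objective is safety and tolerability, and neither it nor dose escalation uses these tests.

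The conclusion is conditional on the protocol body and SAP. If they specify dose-versus-Naropin estimates, what remains is a wording mismatch in the Synopsis.

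**What to change.** Keep the overall tests. For each efficacy endpoint, add each dose-minus-Naropin estimate with a 95% confidence interval on a matching scale:

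- a mean difference where ANOVA is used, or a rank-based shift where Kruskal-Wallis is used;
- a hazard ratio for time to first rescue;
- a risk difference for proportions.

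Pool the Naropin subjects, since the comparator is the same 150 mg in every cohort, and say so. Because cohorts are enrolled in sequence, 12 of the 16 pooled controls for any dose come from other cohorts, so add a cohort-adjusted sensitivity analysis. Label the intervals exploratory and unadjusted, and use Dunnett-type simultaneous intervals for any claim of significance. If the protocol body or SAP already does this, align the Synopsis wording only.

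The cost is a few tables and some text, with no new subjects or data. The drawbacks should be stated in the plan. Intervals will be wide: about 0.76 SD per dose unadjusted, 0.96 SD with Dunnett and 1.16 SD cohort-adjusted. The chance of at least one false signal across four unadjusted dose comparisons is about 16% per endpoint, and higher across the several endpoints.

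### PGA is given a chi-square or Fisher's exact test; if PGA is an ordered rating with more than two levels, a rank test would use the ordering and gain some power at little cost

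*Combined protocol and SAP*

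**What the plan says.** In Section 3 Synopsis, under Statistical Analysis, one sentence covers the categorical outcomes: "Chi-square test or Fisher's exact test will be used to assess the overall differences among treatments". It applies to being opioid free, using no rescue analgesic and using no antiemetic, and the list closes with "subjects who used no postoperative antiemetic therapy, and PGA".

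A rank method is already in the same section. ANOVA "or a Kruskal-Wallis test (if the normality assumption is not met) will be used" for the NPRS scores, their AUC and rescue consumption. PGA is not among these.

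On size, "Each cohort will comprise 12 subjects receiving a dose of TLC590 and 4 subjects receiving active comparator drug", and "The study will enroll approximately 64 evaluable subjects who meet all entry criteria across 4 cohorts". The plan adds that "No formal sample size calculation will be performed".

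The Synopsis does not expand the abbreviation PGA, give its number of levels, say whether it is dichotomised, state an alpha for it, or say whether Naropin subjects are pooled across cohorts. Exploratory endpoints are only described, whereas PGA gets a formal test. I therefore read it as one of the measures serving the secondary objective of comparing efficacy with Naropin.

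**The concern.** Chi-square and Fisher's exact tests give the same answer however the categories are arranged. If PGA runs from poor to excellent, or similar, a steady movement towards better ratings counts no more than an arbitrary scatter of the same size. The test also spreads its degrees of freedom over many sparse cells. With 12 subjects per dose there is little information to spare, and a real improvement over Naropin could go undetected more often than it needs to.

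What is at stake is sensitivity on one secondary efficacy measure. Neither the validity of the test nor the safety of the trial is in question.

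**Working it through.** **Inputs from the Synopsis.** There are four cohorts of 12 TLC590 and 4 Naropin subjects: 4 × (12 + 4) = 64, which agrees with the stated total. If Naropin is pooled, the groups are 4 × 4 = 16 and four of 12. The plan states no power, alpha or effect for PGA, so there is no figure to reproduce.

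**Assumptions (not in the Synopsis).** Naropin pooled; four ordered categories with Naropin probabilities 0.15/0.35/0.35/0.15; a proportional-odds shift with log odds ratio rising in equal steps to the top dose; alpha 0.05.

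**Degrees of freedom and sparsity.** For a 5 × 4 table, chi-square has (5 − 1)(4 − 1) = 12 degrees of freedom and Kruskal-Wallis has 5 − 1 = 4. With no effect, the expected counts are 12 × 0.15 = 1.8 and 12 × 0.35 = 4.2 in the dose groups, and 16 × 0.15 = 2.4 and 16 × 0.35 = 5.6 for Naropin. Only 2 of the 20 cells reach 5.

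**Power by simulation (Pearson chi-square versus tie-corrected Kruskal-Wallis).**

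| Top-dose odds ratio | Chi-square | Kruskal-Wallis | Difference (points) |
|---|---|---|---|
| 2 | 7% | 10% | 3 |
| 3 | 13% | 22% | 9 |
| 4.5 | 22% | 40% | 18 |
| 7.4 | 40% | 65% | 25 |

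With the same odds ratio of 4.5 at every dose, power is about 31% versus 56%. With no effect, both tests reject about 4–5% of the time, so the gain does not come from inflated type I error.

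**Other scales.** With two other four-category distributions and one five-category distribution, and top-dose odds ratios from 3 to 10, chi-square power is 11–55% and Kruskal-Wallis 22–80%, a loss of about 9–33 points.

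**Fisher instead of chi-square.** On those same distributions at odds ratio 6, a permutation version of the chi-square test, standing in for the exact test, gave 29–37%. Kruskal-Wallis gave 51–57%. Exactness does not recover the lost ordering.

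**If PGA is binary.** Mid-ranks are then a linear function of the 0/1 outcome. The tie-corrected Kruskal-Wallis statistic is (N − 1) times the between-group share of the total sum of squares, and that share equals the Pearson statistic divided by N. So H = X² × (N − 1)/N, and with N = 64 the factor is 63/64 = 0.984. In simulation at odds ratio 6, power is about 40% for chi-square and 38% for Kruskal-Wallis.

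**If the difference is not a shift.** Take all doses at 0.35/0.15/0.15/0.35, with more ratings at both extremes. Power is then about 37% for chi-square and 6% for Kruskal-Wallis.

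**The case against.** The strongest reply is that no error has been shown. The sentence speaks of proportions, and PGA stands beside three yes/no outcomes, so a dichotomised PGA fits the wording. In that case the planned test is suitable. This stands, and it is why the point is conditional. A reader might infer that the plan certainly applies an unordered test to an ordered scale and forfeits a large share of its power. The Synopsis does not support that, because it never gives the scale.

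The size is also open to challenge. Naropin is an active comparator, so large odds ratios are not a given. At 2 or below, both tests have almost no power and the choice hardly matters. Pooling Naropin is an assumption too; without it, power is lower for every test. All of this stands.

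Kruskal-Wallis is not a cure either. It ignores dose order and, in the rising-shift scenarios at odds ratios 4.5 and 7.4, still misses the effect 60% and 35% of the time (100 − 40 and 100 − 65). A non-significant PGA result would remain weak evidence of no difference.

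Finally, a reader might suppose the change has no downside. The extreme-ratings example shows otherwise, though it is a deliberately severe case.

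What the reply does not remove is that the rank test gains power if PGA has several ordered levels and ratings shift, and costs almost nothing if PGA is binary.

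**Conclusion.** The point holds as a conditional, minor improvement. The Synopsis gives PGA an unordered test and names no ordinal method for it. If PGA has more than two ordered levels and treatment shifts the ratings, the loss against Kruskal-Wallis is about 3 points of power at a top-dose odds ratio of 2, rising to about 25 points at 7.4. These figures rest on the assumed four-level scale, the Naropin distribution, pooling, proportional odds and alpha 0.05. If PGA is binary, the loss is essentially nil.

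A reader might go further and conclude that the planned PGA test is invalid or that the trial's conclusions are at risk. The documents do not support this. Type I error is held near 5%, the primary objective is safety and tolerability, and escalation is decided on adverse events, with PK data also reviewed. Cohort size was set for tolerability and PK without any claim of efficacy power.

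**What to change.** Take PGA out of the chi-square/Fisher list. State its scale, and analyse it with the tie-corrected Kruskal-Wallis test or the equivalent row-mean-score test with rank scores. Tabulate the count and percentage in each category by treatment.

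The cost is one sentence in the analysis section, with no new data and no change to conduct. The trade-off is lower sensitivity to differences in spread rather than location; the category table would show such a pattern descriptively.
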